- a. Medical risks, listing all procedures, their major and minor risks and expected frequency. Medical risks are minimal as the study participants will be in control of the treatment plan. No procedures or medical treatments will be provided to the study participants.

The risks associated with the intervention are negligible and mainly pertain to patient confidentiality. It is possible that the intervention may lead to few patients/ family members demanding more 'face time' from their clinicians to answer questions/address concerns about COPD, and that this demand while an encouraging sign of patient engagement and activation may on few occasions not be welcomed by some clinicians.

It is also possible that a patient may not feel comfortable with the peer mentor leading their group and in that event, we'll make accommodations so that they can get connected with another peer mentor. The peer mentors may get attached to a particular participant who is very sick or dies. In that case the peer mentors are instructed to turn to the clinical social worker leading the program who will provide grief counseling and be there for ongoing support. The monthly meetings that the peer mentors will have will also provide another ongoing source of support.

A Data Safety and Monitoring Board has been established for the study. The Board has 3 researchers and a patient advocate. The researchers have many years of experience in clinical management of COPD, research methodology, and community based research. The patient advocate has COPD and has participated in advocacy efforts led by the COPD Foundation. The board will meet twice a year during the study period. The Board has the responsibility for monitoring study data for evidence of adverse effects attributable to study interventions.

- b. Steps taken to minimize the risks.

None of the patient information will be released to their physician, health care organization, or any other party without the patient's permission. Phone contacts to locate the study subject will not suggest the content of the study. All study data will be stored in locked file cabinets at Johns

Hopkins Armstrong Institute for Safety and Quality (not the clinical sites) . Personal identifiers will be removed as soon as possible.

c. Plan for reporting unanticipated problems or study deviations.

Unanticipated problems will be reported to the IRB per IRB specified guidelines and a log will be kept for unanticipated problems and study deviations. Any participant deaths, whether expected or unexpected, will be promptly reported in accordance with JHM policies, except when the death meets one of the exceptions to prompt reporting criterion.

d. Legal risks such as the risks that would be associated with breach of confidentiality.

There are minimal risks for breach of confidentiality that we would address by taking all possible measures to secure study participants personal health information and restrict access to it. All collected data will be kept in a secure database and secured shared drive. No PHI will be saved on personal devices.

e. Financial risks to the participants.

No financial risks.

10. Benefits

a. Description of the probable benefits for the participant and for society.

All patients in this study may experience benefits from having an in person meeting with a healthcare professional to learn about COPD and evidence based recommendations for their condition, double check their inhaler use technique, and receive educational materials and a community resource guide. They may also benefit from having the opportunity during their 9 month study period to call the RCP and ask questions about COPD and discuss any difficulties in managing it.

Study participants randomized to the HCP PLUS Peer Support arm may benefit from meeting other peers and gaining new knowledge about management of COPD.

This study may bring societal benefits if the developed study intervention was demonstrated later to result in improved outcomes for COPD patients and their caregivers.

11. Payment and Remuneration

a. Detail compensation for participants including possible total compensation, proposed bonus, and any proposed reductions or penalties for not completing the protocol.

1) PATIENT PARTICIPANTS: Participants will receive a total of \$80 over the 9 months study period for his/her time and participation. The compensation will be given as follows: \$20 for the Enrollment visit. The participant will receive \$15 each for completing a phone interview at 3 months, and then at 6-month follow-up. S/he will also receive \$30 for completing the 9-month final follow-up interview.

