iii. Safety Management

The interventions employed in this study are minimal risk interventions where no medical treatments or advice will be provided. All treatment services will remain under the control of the study participants and their healthcare providers. The RCP who will be delivering the HCP intervention, and the social worker who will facilitate the Peer Get-togethers and provide oversight and support for the BREATHE Pals, are both licensed Healthcare professionals who are employed within Johns Hopkins. The roles they will perform in delivering the study interventions are well within their professional scope of practice. These professionals will be trained on intervention procedures and if a study participant requires additional medical treatment or social support services, they will not provide treatment services themselves but rather facilitate the study participant's access to these services at the respective sites where the participants receive their care.

The peer mentors will be specifically trained not to provide any medical advice and to refer study participants who request such advice or report on specific healthcare or social needs to the social worker. The peer mentors, in addition, will be instructed to turn to the social worker with any concerns that they may personally have about any participants, or if they feel distressed or burdened by their BREATHE Pal role. All peer mentors will have the opportunity to regularly meet with the social worker to discuss their volunteer efforts and any needs or concerns that they may have.

Given that many of our study participants will have severe COPD and other co-morbidities, and that frequent hospitalizations and occasional deaths are anticipated in this patient population, we will establish a Data Safety and Monitoring Board (DSMB). The primary responsibilities of the DSMB will include monitoring of participant safety, data quality, and adverse events tracking. The DSMB will meet regularly, either in person, or via conference call. They will receive data reports prior to the meeting that contain information about participant recruitment, retention, participant characteristics and adverse events. In addition to the DSMB members, meeting attendees will also include the study Principal Investigator and the study Biostatistician.

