together, participated in a BREATHE call, or by having a phone conversation with their BREATHE pal containing discussion of COPD-related issues (determination based on BREATHE pal notes.) For a more detailed description of our complier-average causal effect analysis and IV approach, please refer to the statistical analysis plan in the supplemental study documents section (SAP_BREATHE2_2019Jun26).

The sample size calculation will be based on an overall comparison of the change between the baseline and 6-month measurements of the patients on the St. George scale (primary outcome) in the two arms (interaction term). The unadjusted per-arm sample size is based on a power of 0.80, alpha of 0.05, a minimally clinical significant difference in change scores of 4 points and a meta-analysis estimate of variability. The estimated sample size is 145 patients per arm, after accounting for a 15% attrition rate, assuming a within-patient correlation between measurements of 0.8.

Heterogeneity of Treatment Effects (HTE) HT-1

The goal of the HTE analyses in this study is to consider the difference in treatment effect between the two arms, taking into consideration differences in the arms that are not obviously accounted for in the balance created by the randomization scheme. Patient characteristics such as disease severity or caregivers' presence may show differences in the intervention's effect and thus are important avenues to explore for hypothesis generation. In this hypothesis generating HTE analysis, we will consider the following subgrouping variables: age (4 categories), gender, disease severity, baseline PAM score, and caregiver presence. Within the HCP PLUS Peer Support group, we will also consider subgrouping by the propensity for adherence to treatment.

HT-2, HT-3

Subgroup treatment effects will be estimated by including a three-way interaction between the subgroup variable, the study assignment variable, and the 6-month time variable in a generalized linear mixed RE model. We will test for a difference in treatment effect between subgroups by a hypothesis test of the overall three-way interaction in this model. We will report estimates of subgroup treatment effects with corresponding 95% confidence intervals (CIs). For a more detailed description of the heterogeneity of treatment effect, please refer to the statistical analysis plan in the supplemental study documents section (SAP_BREATHE2_2019Jun26).

- d. Early stopping rules.
No early stopping rules.

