The study will compare the impact of these strategies on the outcomes of health-related quality of life, mortality, and use of Emergency Department (ED) and other hospital services, as well as intermediate measures such as patient activation, self- efficacy, and self-care behavior, as described in the BREATHE2 Study Conceptual Model shown in Figure 1 below. At the same time, the study will compare the impact of these strategies on caregiver self-efficacy, stress, and coping skills. We will also assess both patient and caregiver experience and satisfaction within the HCP PLUS Peer Support Group.

[figure not shown]

Figure 1. BREATHE2 Study Conceptual Model

Study Design (PCORI Standard IR-1)

Phase 1 of this study involved intervention development followed by peer mentor recruitment and training. Phase 2 of this study, which is addressed by this SAP, involves rigorous testing of the study intervention in a randomized controlled trial (RCT) at two study sites: (1) Johns Hopkins Bayview Medical Center (JHBMC) and affiliated pulmonary and primary care clinics and (2) Howard County General Hospital (HCGH) and affiliated pulmonary and primary care clinics. (some of these clinics are part of Johns Hopkins Community Physicians). Thus within each study site, patients were recruited from two clinical settings: (1) inpatient recruitment within the hospital and (2) outpatient recruitment from the affiliated clinics.

We consented and enrolled 290 persons who met the initial eligibility criteria of receiving a physician diagnosis of COPD and treatment for it. Patient participants were randomized to one of the two study groups in this trial (HCP or HCP PLUS Peer Support) and their respective Caregiver Participant, if they have one enrolled, participated with them in that study group. Then patients were randomized 1:1 to the HCP or the HCP PLUS Peer Support.

Our primary study outcome is the change in quality of life (QOL) over the 6 months post discharge. Other patient measures include patient activation self-efficacy, self-care behavior,

health status, used of Emergency Department (ED) and other hospital services, and survival. Caregiver measures include caregiver self-efficacy, stress, and coping skills.

Intervention Description

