12. Participation in pulmonary rehabilitation at 3, 6, and 9 months post-enrollment.

Hypothesis: Patients receiving the HCP PLUS Peer Support will have greater level of participation in pulmonary rehabilitation than patients in the *HCP only* group.

13. Change in smoking status at 3, 6, and 9 months post-enrollment.

Hypothesis: Patients receiving the HCP PLUS Peer Support will have a higher smoking cessation rate than patients in the *HCP only* group.

Handling of Missing Data (PCORI [name]-4)

There are two types of missing data, at the respondent level (unit non-response) and at the specific question level (item non-response). At the respondent level, missing data occurred because of patient death, withdrawal from study, or inability to be reached via phone for an interview. Comparisons of missingness by several patient characteristics at baseline will be performed with Fisher's exact or Chi-Square tests to examine any potential systematic pattern to the missing data. For the specific case of the SGRQ instrument, values of 100 (the worst possible QoL score) will be imputed for any assessment in which a patient was not available because of death.

With respect to data at the specific question level, missing data will be handled according to each instrument collection manual. In some cases, for example the SGRQ,¹ PAM,² and PROMIS-anxiety,³ -depression,⁴ -emotional,⁵ and -instrumental support index⁶ score will be prepared in instrument specific calculators, provided by the instrument's authors, and accounted for any assignments of missing scores based on the availability of item responses. Missing data for other instruments such as PROMIS-social isolation⁷ and -informational support index⁸, understanding COPD⁹, and Morisky measure,¹⁰ will be handled according to the instrument's author's direction.

When no information is available for handling missing item responses on a particular instrument, a rule, allowing no more than 25% of the items for the scale/domain to be missing, was used. If less than 25% of the item responses were missing, the mean of the non-missing item responses

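### The 0.80 power in protocol section 7.c makes no allowance for the SAP rule that scores deaths as SGRQ = 100, and it falls materially short unless peer support also cuts mortality by roughly half or more

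*Combined protocol and SAP*

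**What the plan says.** Protocol section 7.c bases the sample size on the comparison of SGRQ change from baseline to 6 months. The inputs are "based on a power of 0.80", an alpha of 0.05, "a minimally clinical significant difference in change scores of 4 points" and "a meta-analysis estimate of variability". The result is: "The estimated sample size is 145 patients per arm, after accounting for a 15% attrition rate, assuming a within-patient correlation between measurements of 0.8". The SD is not given, attrition is not defined, and the paragraph does not mention deaths.

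The SAP, under Handling of Missing Data, names death as one reason for a missing respondent and then sets the rule for the SGRQ: "values of 100 (the worst possible QoL score) will be imputed for any assessment in which a patient was not available because of death". The primary test, in the SAP's Statistical Analysis section, is the group by 6-month interaction in a linear mixed model, so these scores enter it.

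Protocol section 4.a.iii says that "frequent hospitalizations and occasional deaths are anticipated in this patient population" but gives no rate. The SAP's Study Design section reports the final enrolment: "We consented and enrolled 290 persons who met the initial eligibility criteria". That is 2 × 145, so there is no surplus over the calculated size. Neither document returns to the power after the death rule is introduced.

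**The concern.** The variable in the power calculation is not quite the variable that will be tested. Under the SAP rule a patient who dies by 6 months is not lost. That patient contributes an observed change of 100 minus baseline, about +50 points if the baseline is near 50, to a variable whose implied SD is about 11. A few such values inflate the variance of change and pull the baseline to 6-month correlation below 0.8.

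This is the only power claim for the primary endpoint. If the 6-month result is null, a reader will take it as coming from a trial with 80% power to detect 4 points. Under the trial's own scoring rule that may be well off. The point concerns the stated power only. It does not question whether 100 is a suitable score for death.

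**Working it through.** **Step 1. Recover the plan's figure.** The SD is not given, so 145 can be back-solved but not independently reproduced. Two-sided alpha is assumed, since 7.c does not say.

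- Evaluable per arm: 145 × 0.85 = 123.25.
- SD of change = 4 / [(1.960 + 0.842) × √(2/123.25)] = 11.2.
- SD of the score at correlation 0.8 = 11.2 / √(2 × 0.2) = 17.7.

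A score SD of 17.7 returns 123 evaluable and 145 enrolled per arm, so the stated size is consistent with its inputs. With one-sided alpha the implied SD of change would be 12.6.

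**Step 2. Add deaths scored 100.** Let p be the proportion of an arm that dies by 6 months. Keep 123.25 survivors per arm and add the deaths. This favours the plan: if the 123 already included the deaths, fewer patients would be analysed and power would be slightly lower.

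- Analysed per arm: n = 145 × (0.85 + p).
- Share of those who died: q = p / (0.85 + p).
- Mean change: 0 in HCP survivors, −4 in peer-support survivors, 100 − m in those who die, where m is the mean baseline SGRQ (assumed 50, range 40 to 60).
- Variance in an arm = (1 − q) × 11.2² + q × 17.7² + q(1 − q) × G², where G is the gap between mean change in deaths and in survivors. At m = 50, G is 50 in the HCP arm and 54 in the peer-support arm.
- Power = Φ(difference / SE − 1.960).

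Worked case, 2% deaths in both arms, m = 50: q = 0.02/0.87 = 0.0230 and n = 126.15. The variances are 13.6² and 14.0², so SE = √[(13.6² + 14.0²)/126.15] = 1.74. The difference is 4 × (1 − 0.0230) = 3.91. The ratio is 2.25 and power is Φ(0.29) = 0.61.

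**Step 3. Equal mortality in both arms.**

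| Deaths by 6 months | SD of change (HCP arm, m = 50) | Correlation (simulated) | 95% CI half-width, points | Power, m = 50 (m = 40 to 60) |
|---|---|---|---|---|
| 0% | 11.2 | 0.80 | 2.8 | 0.80 |
| 1% | 12.5 | 0.77 | 3.1 | 0.70 (0.66 to 0.73) |
| 2% | 13.6 | 0.74 | 3.4 | 0.61 (0.56 to 0.66) |
| 5% | 16.3 | 0.66 | 4.0 | 0.45 (0.38 to 0.52) |

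One percent of 290 is about three patients.

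**Step 4. Lower mortality with peer support.** Deaths now add to the difference as well as to the variance.

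| HCP v peer support | Difference (m = 50) | Power, m = 50 (m = 40 to 60) |
|---|---|---|
| 5% v 4% | 4.35 | 0.58 (0.52 to 0.64) |
| 5% v 3% | 4.94 | 0.71 (0.67 to 0.75) |
| 4% v 2% | 5.01 | 0.77 (0.74 to 0.80) |
| 10% v 5% | 6.26 | 0.80 (0.77 to 0.83) |

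At m = 50, a full return to 0.80 needs a mortality ratio of about 0.40 when HCP-arm mortality is 1%, 0.42 at 2%, 0.46 at 5% and 0.50 at 10%.

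**Step 5. Baseline adjustment.** The SAP adjusts for baseline, which the change-score calculation ignores. In simulation (6,000 trials per scenario, m = 50, equal mortality), power without and with adjustment was 0.79 and 0.83 at no deaths, 0.69 and 0.73 at 1%, 0.61 and 0.64 at 2%, and 0.45 and 0.47 at 5%. Adjustment adds about 2 to 4 points and does not restore what the deaths remove.

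**The case against.** **The trial hypothesises better survival with peer support.** Section 7.c, SAP Study Objectives item (b) and SAP secondary outcome 6 all say so. A reader might infer that 0.80 power holds only if nobody dies by 6 months. That would be wrong: under the death rule a survival benefit adds to the tested difference, and roughly halving mortality brings power back close to 0.80. This objection stands and limits the claim. But the documents give no size for the mortality effect, 7.c is powered on 4 SGRQ points alone, and a modest benefit (5% v 4%) leaves about 0.58.

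**Every quantity behind the size is assumed.** The SD is back-solved, and mortality and baseline mean are not in the documents. A reader might conclude that the design certainly delivers less than 80%. The documents cannot settle that, so only a conditional statement is supported. The direction under equal mortality is the same at every baseline mean from 40 to 60.

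**Section 7.c does not say that deaths are attrition.** It is tempting to read the 15% that way, but the paragraph leaves attrition undefined. Nor is there an arithmetic slip: 145 fits its stated inputs. The gap is a SAP rule that was not carried back to the power statement.

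**Sicker patients may be the ones who die.** Their jump to 100 would then be smaller. A simulation of that case gave 0.73, 0.67 and 0.55 at 1%, 2% and 5% deaths (change scores, mean 50). The loss is milder but remains.

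**Enrolment is complete and nothing says that power will be used to read a null result.** This is fair, and it is why the remedy is confined to the wording.

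**Conclusion.** The point holds in conditional form. The 0.80 power in 7.c does not reflect the SAP's scoring of deaths. Unless peer support also cuts mortality by roughly half or more, power for a 4-point difference is materially below 0.80. The Step 3 and Step 4 figures show the possible size; they are not an estimate of this trial's actual power. They rest on two-sided alpha, the back-solved SD, an assumed baseline mean and mortality, and a normal approximation to a two-time-point change score in place of the planned mixed model. Any power regained through a survival benefit would come partly from deaths, not from the 4-point quality-of-life effect on which 7.c bases its figure.

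**What to change.** Restate the power paragraph in protocol section 7.c and carry it into the SAP, which at present has none:

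- Give the SD taken from the meta-analysis, the baseline SGRQ mean and whether alpha is two-sided.
- Say whether the 15% attrition includes deaths. Under the SAP rule it should cover living non-responders only.
- Report power under the death = 100 rule over a stated mortality range, for equal and for unequal mortality by arm.
- Drop the unqualified 80% figure, and do not replace it with a statement that 0.80 requires no deaths.
- State that a null primary result will be interpreted by its confidence interval.

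Enrolment, data collection and the primary test stay as they are. The cost is one paragraph and a less favourable stated power.

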The study will compare the impact of these strategies on the outcomes of health-related quality of life, mortality, and use of Emergency Department (ED) and other hospital services, as well as intermediate measures such as patient activation, self- efficacy, and self-care behavior, as described in the BREATHE2 Study Conceptual Model shown in Figure 1 below. At the same time, the study will compare the impact of these strategies on caregiver self-efficacy, stress, and coping skills. We will also assess both patient and caregiver experience and satisfaction within the HCP PLUS Peer Support Group.

[figure not shown]

Figure 1. BREATHE2 Study Conceptual Model

Study Design (PCORI Standard IR-1)

Phase 1 of this study involved intervention development followed by peer mentor recruitment and training. Phase 2 of this study, which is addressed by this SAP, involves rigorous testing of the study intervention in a randomized controlled trial (RCT) at two study sites: (1) Johns Hopkins Bayview Medical Center (JHBMC) and affiliated pulmonary and primary care clinics and (2) Howard County General Hospital (HCGH) and affiliated pulmonary and primary care clinics. (some of these clinics are part of Johns Hopkins Community Physicians). Thus within each study site, patients were recruited from two clinical settings: (1) inpatient recruitment within the hospital and (2) outpatient recruitment from the affiliated clinics.

We consented and enrolled 290 persons who met the initial eligibility criteria of receiving a physician diagnosis of COPD and treatment for it. Patient participants were randomized to one of the two study groups in this trial (HCP or HCP PLUS Peer Support) and their respective Caregiver Participant, if they have one enrolled, participated with them in that study group. Then patients were randomized 1:1 to the HCP or the HCP PLUS Peer Support.

Our primary study outcome is the change in quality of life (QOL) over the 6 months post discharge. Other patient measures include patient activation self-efficacy, self-care behavior,

health status, used of Emergency Department (ED) and other hospital services, and survival. Caregiver measures include caregiver self-efficacy, stress, and coping skills.

Intervention Description

All study participants will receive a Health Care Professional (HCP) support intervention in this study, which involves a 1 hour session with the respiratory care practitioner (RCP), and the ability to follow up with them with any questions. They would also receive the BREATHE binder with educational materials on COPD self-management and a resource guide.

Those randomized to the HCP PLUS Peer Support group of the study will also have the opportunity to participate in a Peer Support Program. This program will offer patients and their caregiver support services to be delivered via multiple channels including one-on-one and group conversations. In this program, the patient and caregiver participants will have the option to connect with other peers. Each patient and caregiver participant in this study group will be *matched* with a peer mentor (referred to as BREATHE Pal). The BREATHE pal will talk with the participant at regular intervals at peer group *Get together* events and/ or via phone. The group events will take place at the study sites, and will be co-led by two BREATHE Pals in the presence of a social worker. At these events, select topics about COPD self-management will be discussed, and the messages delivered by the respiratory care practitioner will be reinforced. Participants who are unable to attend these in-person events have the option to participate in BREATHE calls, where the same topics are discussed via a conference call.

Study Objectives

We hypothesize that the dual strategy of using *HCP PLUS Peer Support* to engage and support COPD patients and caregivers will have superior outcomes to the *HCP only* strategy at 3-, 6-, and 9-months post enrollment compared to baseline in the following areas:

- a) Improved health- related quality of life measured with the St. George's Respiratory Questionnaire.
- b) Improved survival and reduced numbers of COPD-related hospital and ED visits.

- c) Improved patient activation, self-efficacy, and self-care behaviors

Data Collection for Phase 2

All participants will be interviewed in person, upon enrollment, prior to randomization, by a trained study team member. At the enrollment visit, baseline data will be collected on demographics, bio-psychosocial status, as well as COPD knowledge, self-management skills, patient activation, and health literacy levels. Participants will then be interviewed via phone by a research team member, who is blinded to their study group assignment at 3-, 6-, and 9-months post enrollment. Similarly, we will collect data from caregiver participants who will be surveyed upon enrollment, and at 3-, 6-, and 9-months follow up post enrollment. Due to the study end date, it will not be possible to collect 9-month follow-up data for participants who enrolled later in the study.

Additionally, information will be collected post enrollment on whether the patient has visited the ED or been re-hospitalized via Chesapeake Regional Information System for our Patients (CRISP). CRISP will be used determine whether the visit was COPD-related using a set of pre-determined discharge diagnoses.

Study Outcomes and Hypotheses

The study groups will be compared for the following outcomes:

Primary Outcome for Patient Participants:

1. Change in health-related quality of life (HRQOL) as measured by the St. George Respiratory Questionnaire (SGRQ) total score, from baseline to 6 months post-enrollment.

Hypothesis: Patients in the HCP PLUS Peer Support group will have a larger improvement in HRQOL (larger negative change in SGRQ score) at 6 months post discharge compared to baseline, than patients in the *HCP only* group.

Secondary Outcomes and Intermediate Measures for Patient Participants:

Secondary Outcomes:

1. Change in HRQOL based on SGRQ total score at 9 months post enrollment.

Hypothesis: Patients in the HCP PLUS Peer Support group will have larger improvement in HRQOL (larger negative change in SGRQ score) compared to baseline, than patients in the *HCP only* group.

2. Total number of COPD-related hospitalizations and ED visits at 3, 6, and 9 months post-enrollment.

Hypothesis: Patients receiving the HCP PLUS Peer Support will have a lower rate of COPD-related hospitalizations and ED visits than patients in the *HCP only* group.

3. Total combined number of *all cause* hospitalizations and ED visits at 3, 6, and 9 months post-enrollment.

Hypothesis: Patients receiving the HCP PLUS Peer Support will have a lower rate of hospitalizations and ED visits than patients in the *HCP only* group.

4. Total combined number of *all cause* hospitalizations and ED visits at 3, 6, and 9 months post-enrollment.

Hypothesis: Patients receiving the HCP PLUS Peer Support will have a lower total number of *all cause* hospitalizations and ED visits than patients in the *HCP only* group.

5. Change in HRQOL based on SGRQ domain scores at 3, 6, and 9 months post-enrollment.

Hypothesis: Patients receiving the HCP PLUS Peer Support will have larger improvement in HRQOL (larger negative change in SGRQ score) compared to baseline, than patients in the *HCP only* group.

6. Mortality rate at 3, 6, and 9 months post-enrollment.

Hypothesis: Patients receiving the HCP PLUS Peer Support will have a lower mortality rate compared to patients in the *HCP only* group.

Intermediate Measures:

7. Change in PROMIS support domain scores (Instrumental, Informational, Depression, Anxiety, Social Isolation, and Emotional Support) at 3, 6, and 9 months post-enrollment.

Hypothesis: Patients receiving the HCP PLUS Peer Support will have larger positive change in PROMIS scores compared to baseline, than patients in the *HCP only* group.

8. Change in Herth Hope Index total score at 3, 6, and 9 months post-enrollment.

Hypothesis: Patients receiving the HCP PLUS Peer Support will have larger positive change in Hearth Hope Index scores compared to baseline, than patients in the *HCP only* group.

9. Change in Patient Activation Measure (PAM) scores at 3, 6, and 9 months post-enrollment.

Hypothesis: Patients receiving the HCP PLUS Peer Support will have larger positive change in PAM scores compared to baseline, than patients in the *HCP only* group.

10. Change in patient's understanding and self-efficacy, as measured by the *Understanding COPD questionnaire's* three components (About COPD, Symptom Management, and Accessing Help and Support) at 3, 6, and 9 months post-enrollment.

Hypothesis: Patients receiving the HCP PLUS Peer Support will have larger positive change in understanding and self-efficacy levels compared to baseline, than patients in the *HCP only* group.

11. Morisky adherence levels at 6 months post-enrollment.

Hypothesis: Patients receiving the HCP PLUS Peer Support will have a higher level of adherence compared to patients in the *HCP only* group.

12. Participation in pulmonary rehabilitation at 3, 6, and 9 months post-enrollment.

Hypothesis: Patients receiving the HCP PLUS Peer Support will have greater level of participation in pulmonary rehabilitation than patients in the *HCP only* group.

13. Change in smoking status at 3, 6, and 9 months post-enrollment.

Hypothesis: Patients receiving the HCP PLUS Peer Support will have a higher smoking cessation rate than patients in the *HCP only* group.

Handling of Missing Data (PCORI [name]-4)

There are two types of missing data, at the respondent level (unit non-response) and at the specific question level (item non-response). At the respondent level, missing data occurred because of patient death, withdrawal from study, or inability to be reached via phone for an interview. Comparisons of missingness by several patient characteristics at baseline will be performed with Fisher's exact or Chi-Square tests to examine any potential systematic pattern to the missing data. For the specific case of the SGRQ instrument, values of 100 (the worst possible QoL score) will be imputed for any assessment in which a patient was not available because of death.

With respect to data at the specific question level, missing data will be handled according to each instrument collection manual. In some cases, for example the SGRQ,¹ PAM,² and PROMIS-anxiety,³ -depression,⁴ -emotional,⁵ and -instrumental support index⁶ score will be prepared in instrument specific calculators, provided by the instrument's authors, and accounted for any assignments of missing scores based on the availability of item responses. Missing data for other instruments such as PROMIS-social isolation⁷ and -informational support index⁸, understanding COPD⁹, and Morisky measure,¹⁰ will be handled according to the instrument's author's direction.

When no information is available for handling missing item responses on a particular instrument, a rule, allowing no more than 25% of the items for the scale/domain to be missing, was used. If less than 25% of the item responses were missing, the mean of the non-missing item responses

was calculated and was used to replace the value of the missing item responses before calculation of the scale/domain score. This approach weights the scale/domain score towards the respondent's mean response and is balanced by requiring a large majority of item responses to be available. If more than 25% of the item responses were missing, the scale/domain score was considered missing.

Statistical Analysis (PCORI Standard IR-1, RC-4)

Statistical summaries and distributions of patient characteristics will be reviewed by study site (JHBMC and HCGH) and by recruitment setting (inpatient and outpatient). Statistical summaries and distributions of patient and clinical characteristics will also be reviewed across study groups. Randomization of the patients to the study groups expects that on average the groups were balanced on characteristics that might affect the study results, such as socio-demographic and health status. Thus, no statistical tests to compare the groups on patient characteristics will be performed.¹¹

Exploratory analyses will be performed cross-sectionally at baseline, 3, 6, and 9 months post-discharge for each of the outcomes across the two study groups. This will provide an assessment of the outcomes' distributions, missingness patterns and the need for additional data review and quality assurance.

The main analysis approach for assessing the change in the primary outcome measure from baseline, as well as changes in secondary outcome measures from baseline, will consist of performing analyses of the treatment effect between the two study groups under intention to treat (ITT) adjusted for baseline measure, site, and recruitment setting.

Repeated outcomes in this study will be evaluated using generalized linear mixed random-effects (RE) models. The generalized linear mixed RE model reflects the study's interest in comparisons of change at the individual level, where the changes may be subject-specific and reflective of potentially unmeasured variables. This model also fits well with the approaches related to

missing data and heterogeneity of treatment effects discussed below. In particular, this approach will help us handle the missing 9-month data for participants who enrolled later in the study.

The primary repeated outcome (SGRQ) will be evaluated using a linear mixed RE model. Within this model, the primary hypothesis about change in HRQOL from baseline to 6 months, will be evaluated by a hypothesis test of the interaction term between study group and the 6-month time variable.

For secondary outcomes, we will fit appropriate generalized linear mixed RE models based on the type of outcome variable. Continuous measures, such as for HERTH Hope Index or PROMIS support domain scores, will be assessed using linear mixed RE models. Binary outcomes, such as Morisky adherence to medication, will be assessed using logistic mixed RE models. Outcomes that are cumulative counts, such as number of hospitalizations and ED visits, will be assessed using Poisson or negative binomial mixed RE models, as appropriate. Differences in change in outcome from baseline to 3, 6, and 9-months between the study groups will be assessed by including interaction terms between the time variables and study group. We will assess significance by first testing the overall interaction between time and group. If the overall interaction is significant for an outcome measure, we will then estimate and test individual time differences accounting for multiple testing using a Bonferroni correction. Initially models will be adjusted only for baseline measure, site, and recruitment setting. We will also consider adjusting for patient characteristics such as age, gender, presence of caregiver, home oxygen use, and prior hospitalization.

Unadjusted survival analyses using Kaplan-Meier and log rank tests will be performed for *time to death or first COPD-related hospitalization or ED visit*. Statistical significance will be considered for $p < 0.05$.

Complier-Average Causal Effect (CACE) using Instrumental Variable Estimation

CACE: Primary Outcome

